10.0 Analysis Items and Method

10.1 Patient Disposition Items

Compile information including the number of enrolled patients, number of patients with eCRFs collected, numbers of safety- and efficacy-evaluable patients, and the number of patients excluded from analysis and reasons for exclusion.

10.2 Patient Demographics

Compile patient demographic information including sex, age, hypersensitivity disposition, and complications.

10.3 Treatment Details

Compile information on administration of the Drug and of concomitant medications.

10.4 Safety Items

Compile the following regarding the safety-evaluable population. AEs, coded using MedDRA, will be summarized by preferred term (PT) and by system organ class (SOC).

10.4.1 Onset Status of Adverse Events

Compile the incidence of AEs occurring during the observation period, in terms of, e.g., causal relationship with the Drug, type, seriousness. Note that bleeding-related events should be separately compiled because such events are set as a priority survey item.

10.4.2 Factors Likely to Affect Safety

Compile the incidence of ADRs occurring during the observation period, by stratification variables: patient baseline characteristics (sex, age, presence or absence of renal

dysfunction, presence or absence of hepatic dysfunction, etc.) and treatment regimen (administration of the Drug, administration of concomitant medications such as anticoagulant drugs, antiplatelet drugs).

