3.0 Target Sample Size and Rationale for Sample Size Setting

3.1 Target Sample Size

3,000 patients

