3.2 Rationale for Sample Size Setting

Bleeding-related events are set as a priority survey item for the Drug. As postmarketing surveillance of EPA products in antihyperlipidemic therapy has reported that the incidence of bleeding-related ADRs was 0.4% and that the percentage of anticoagulant and antiplatelet concomitant use was about 10%, the Study sets a target of 3,000 patients so that anticoagulant and antiplatelet concomitant use can be assessed to some degree, in addition to bleeding-related ADRs.

Note that this rationale for the sample size is not based on statistical evidence.

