Details of Statistical Analysis	
Compile the following items for the prior-approval status and per survey unit period of the special drug use surveillance.
 
Statistical analysis of ‘number of study sites,’ ‘number of surveyed patients,’ ‘number of patients with ADRs,’ and ‘number of ADRs’ should cover safety-evaluable patients locked during each survey unit period.
 
  
 Item Name	Details of Statistical Analysis	
   
 Number of study sites	Number of medical institutions that have collected eCRFs	
 
 Number of surveyed patients	Number of safety-evaluable patients.	
 
 Number of patients with ADRs	Number of patients in which ADRs occurred.	
 
 Number of ADRs	Number of ADRs that occurred. Every PT occurring should be counted as one event.	
 
 Rate of patients with ADRs	Calculated by the following equation: $[\text{Number of Patients with ADRs}] / [\text{Number of Safety-Evaluable Patients}] \times 100$	
 
 ADR type	 
The calculation method in performing each analysis should be as follows:
 
[Number of patients with ADRs]
 
 Number of patients in which ADRs occurred. 
[Number of ADRs]
 
 Number of ADRs that occurred. If the same ADR occurs more than once in the same patient, a total of frequencies of the ADR should be counted. 
[Rate of patients with ADRs]
 
 Calculated by the following equation: $[\text{Number of Patients with ADRs}] / [\text{Number of Safety-Evaluable Patients}] \times 100$. 
[ADR type]
 
 ADRs should be replaced by MedDRA terms. Categorize by SOC and compile ADRs by PT in each category. If SOC is ‘Investigations,’ classify by HLG (sort by HLG code in ascending order but without outputting) and compile ADRs by PT. 
 At SOC level, the numbers and rates of patients with ADRs should be presented by SOC internationally agreed order. If the same SOC occurs more than once in the same patient, ADRs should be counted as one patient in the SOC. At PT level, the numbers and rates of patients with ADRs should be presented by PT code in 	
  
	Item Name	Details of Statistical Analysis	Number of study sites	Number of medical institutions that have collected eCRFs	Number of surveyed patients	Number of safety-evaluable patients.	Number of patients with ADRs	Number of patients in which ADRs occurred.	Number of ADRs	Number of ADRs that occurred. Every PT occurring should be counted as one event.	Rate of patients with ADRs	Calculated by the following equation: $[\text{Number of Patients with ADRs}] / [\text{Number of Safety-Evaluable Patients}] \times 100$	ADR type	
The calculation method in performing each analysis should be as follows:
 
[Number of patients with ADRs]
 
 Number of patients in which ADRs occurred. 
[Number of ADRs]
 
 Number of ADRs that occurred. If the same ADR occurs more than once in the same patient, a total of frequencies of the ADR should be counted. 
[Rate of patients with ADRs]
 
 Calculated by the following equation: $[\text{Number of Patients with ADRs}] / [\text{Number of Safety-Evaluable Patients}] \times 100$. 
[ADR type]
 
 ADRs should be replaced by MedDRA terms. Categorize by SOC and compile ADRs by PT in each category. If SOC is ‘Investigations,’ classify by HLG (sort by HLG code in ascending order but without outputting) and compile ADRs by PT. 
 At SOC level, the numbers and rates of patients with ADRs should be presented by SOC internationally agreed order. If the same SOC occurs more than once in the same patient, ADRs should be counted as one patient in the SOC. At PT level, the numbers and rates of patients with ADRs should be presented by PT code in

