Details of Statistical Analysis	
Categorize adverse drug reactions (bleeding-related events) by the following categories for each item, and count the types of adverse drug reactions (bleeding-related events). The categories and the compilation method of adverse drug reactions are the same as described in section 2.4.5.

Figure/Table No.	Table 2.4.7

2.4.8 Rate of Patients of Adverse Drug Reactions or Infections by Patient Demographics and Treatment

Details

Statistical Analysis Set	Safety-evaluable patients in this special drug use surveillance	
Details of Statistical Analysis	Categorize ADRs by the following categories for each item and compile the rate of patients with ADRs.	
	Item Name	Category
	Sex	Male, Female
	Age	Minimum age to 64 years, 65 to 74 years, 75 years to maximum age, Unknown
	BMI	Less than 18.5 kg/m ² , 18.5 to less than 25 kg/m ² , 25 to less than 30 kg/m ² , 30 kg/m ² or over, unknown
	Complications	No, Yes
	Complication breakdown	Hypertension, Diabetic, Liver disorder, Kidney disorder, Cardiac disorders Cerebrovascular diseases, Bleeding-related event, Others
	Fasting triglyceride at baseline (mg/dL)	Less than 150 mg/dL, 150 to less than 400 mg/dL, 400 to less than 500 mg/dL, 500mg/dL or over, Not measured
		Less than 150 mg/dL, 150 to less than 400mg/dL, 400 to less than 500 mg/dL, 500 to less than 750 mg/dL, 750 mg/dL or over, Not measured
	Random triglyceride at baseline (mg/dL)	Less than 150 mg/dL, 150 to less than 400 mg/dL, 400 to less than 500 mg/dL, 500mg/dL or over, Not measured
		Less than 150 mg/dL, 150 to less than 400mg/dL, 400 to less than 500 mg/dL, 500 to less than 750 mg/dL, 750 mg/dL or over, Not measured
	Initial dose	2 g, 4 g, other
	Breakdown of presence of change in daily dose	2 g → 4 g, 4 g → 2 g, Other
	Presence or absence of concomitant antihyperlipidemic drug use (during observation period)	No, Yes

	Breakdown of concomitant antihyperlipidemic drugs (during observation period)	statins drugs, fibrate drugs, intestinal transporter inhibitors, anion-exchange resin, nicotinic acid derivatives, probucol, ethyl icosapentate (EPA), others
	Presence or absence of concomitant anticoagulant/antiplatelet drug use (during observation period)	No, Yes
	Breakdown of concomitant anticoagulant/antiplatelet drugs (during observation period)	Anticoagulant drugs, antiplatelet drugs
Figure/Table No.	Table 2.4.8	

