2.4.10 Onset Status of Adverse Drug Reactions or Infections by Age Group

Statistical Analysis Set	Safety-evaluable patients in this special drug use surveillance
Details of Statistical Analysis	Classify the patient population into 64 years or below, 65 to 74 years, and 75 years or over, and compile ADR types. The compilation method of ADR types is the same as described in section 2.4.1.
Figure/Table No.	Table 2.4.10

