2.4.18 Onset Status of Adverse Drug Reactions or Infections by Presence or Absence of Cerebrovascular Complications

Statistical Analysis Set	Safety-evaluable patients in this special drug use surveillance
Details of Statistical Analysis	Compile ADR types by presence or absence of cerebrovascular complications. The compilation method of ADR types is the same as described in section 2.4.1.
Figure/Table No.	Table 2.4.18

2.4.19 Onset Status of Adverse Drug Reactions or Infections by Presence or Absence of Bleeding-related Event Complications

Statistical Analysis Set	Safety-evaluable patients in this special drug use surveillance
Details of Statistical Analysis	Compile ADR types by presence or absence of bleeding-related event complications. The compilation method of ADR types is the same as described in section 2.4.1.
Figure/Table No.	Table 2.4.19

2.4.20 Onset Status of Adverse Drug Reactions or Infections by Presence or Absence of Concomitant Anticoagulant and/or Antiplatelet Drugs

Statistical Analysis Set	Safety-evaluable patients in this special drug use surveillance
Details of Statistical Analysis	Compile ADR types by presence or absence of concomitant anticoagulant or antiplatelet drugs (Concomitant anticoagulant / antiplatelet , Anticoagulant only, Antiplatelet only, Neither). The compilation method of ADR types is the same as described in section 2.4.1.
Figure/Table No.	Table 2.4.20

2.4.21 Onset Status of Adverse Drug Reactions (Bleeding-Related Events) by Presence or Absence of Concomitant Anticoagulant and/or Antiplatelet Drugs

Statistical Analysis Set	Safety-evaluable patients in this special drug use surveillance
Details of Statistical Analysis	Compile the types of adverse drug reactions (bleeding-related events) by presence or absence of concomitant anticoagulant or antiplatelet drugs (Concomitant anticoagulant / antiplatelet , Anticoagulant only, Antiplatelet only, Neither). The compilation method of the types of adverse drug reactions is the same as described in section 2.4.1.
Figure/Table No.	Table 2.4.21

2.4.22 Onset Status of Adverse Drug Reactions or Infections by Baseline Fasting Triglyceride Level

Statistical Analysis Set	Safety-evaluable patients in this special drug use surveillance whose fasting triglyceride levels were measured at baseline

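### ADR rates by factor are crude, and none separates antithrombotic use or organ complications from age; an age- and sex-stratified risk ratio would be a cheap addition

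*Protocol*

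**What the plan says.** Protocol 10.4.2 (Factors Likely to Affect Safety) gives one instruction: "Compile the incidence of ADRs occurring during the observation period, by stratification variables". The variables it names include sex, age, renal and hepatic dysfunction, and use of anticoagulant and antiplatelet drugs.

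The current SAP, which is the first in the file, implements this in two ways. Section 2.4.8 reads "Categorize ADRs by the following categories for each item and compile the rate of patients with ADRs". Sections 2.4.9 to 2.4.33 then break ADR types down by sex, age, BMI, each complication, antithrombotic use, baseline triglyceride, dose and each lipid drug. The rate defined in 2.4.1 is a plain proportion of safety-evaluable patients.

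The age table (2.4.10) uses age alone: "Classify the patient population into 64 years or below, 65 to 74 years, and 75 years or over, and compile ADR types". The antithrombotic tables (2.4.20 and 2.4.21) use four levels, "Concomitant anticoagulant / antiplatelet , Anticoagulant only, Antiplatelet only, Neither", so they cross the two drug classes with each other but with nothing else. No regression, standardised rate, stratified estimate or age-by-antithrombotic table is planned.

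Protocol 3.2 explains the target of "3,000 patients" partly by saying it was chosen "so that anticoagulant and antiplatelet concomitant use can be assessed to some degree". It adds that the number has no statistical basis.

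**The concern.** In routine care, patients on antithrombotic drugs may well be older and have more cardiac, cerebrovascular or kidney disease than those not on them. If ADR risk also rises with age, the Yes and No rows for antithrombotic use in SAP 2.4.8 differ for a reason unrelated to those drugs. The same holds for the organ-complication rows. Under a heading about factors that affect safety, a reader will naturally take the higher rate as the factor's own effect. An offsetting imbalance could equally hide a real effect.

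This bears on antithrombotic co-use, which the sample-size section singles out for assessment. The variables needed to separate it from age are already collected and categorised.

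**Working it through.** **Check of the plan's own figure.** Protocol 1.0 gives 91 of 948 patients with an ADR: 91/948 = 9.6%, as stated. The target of 3,000 cannot be reproduced, because no formula is given.

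**Inputs from the documents.** N = 3,000 (Protocol 3.1); antithrombotic use about 10% and bleeding ADRs 0.4% (Protocol 3.2); any ADR 9.6% (Protocol 1.0, pre-approval patients).

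**Assumed, not in the documents.** The share aged 65 or over among users (p1) and non-users (p0), and the ratio k of ADR risk at 65 or over to that below 65. Antithrombotics are taken to have no effect.

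**Formula.** Crude RR = [1 + p1(k − 1)] / [1 + p0(k − 1)]

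| p1 / p0 | k = 1.5 | k = 2 | k = 3 |
|---|---|---|---|
| 0.60 / 0.40 | 1.30/1.20 = 1.08 | 1.60/1.40 = 1.14 | 2.20/1.80 = 1.22 |
| 0.70 / 0.35 | 1.35/1.175 = 1.15 | 1.70/1.35 = 1.26 | 2.40/1.70 = 1.41 |
| 0.80 / 0.35 | 1.40/1.175 = 1.19 | 1.80/1.35 = 1.33 | 2.60/1.70 = 1.53 |

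The ratio tends to 1 as p1 approaches p0 or k approaches 1. For example, 45% versus 40% with k = 1.5 gives 1.225/1.20 = 1.02.

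**Central case (0.70 / 0.35, k = 2) in patients.**
- Risk below 65: 9.6% / (0.1 × 1.70 + 0.9 × 1.35) = 9.6% / 1.385 = 6.93%. At 65 or over: 13.86%.
- Users: 6.93% × 1.70 = 11.8% of 300, about 35 patients.
- Non-users: 6.93% × 1.35 = 9.4% of 2,700, about 253 patients.
- Difference: 2.4 points. Standard error: √(0.118 × 0.882/300 + 0.094 × 0.906/2,700) = 1.9 points. The spurious difference is about 1.25 standard errors.

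**Effect of stratifying.** Within each age stratum users and non-users have the same risk, so the Mantel-Haenszel ratio is 1.00.

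**The reverse case.** If only antithrombotics act (RR 2) and they are used by 20% of patients aged 65 or over and 5% of younger ones (assumed), a null age factor shows 1.20/1.05 = 1.14.

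**Event counts.**
- Any ADR: 0.096 × 3,000 = 288 patients. At an assumed 2%: 60.
- A model with sex (1), age group (2), four complications (4), antithrombotic use (1) and initial dose (2) has 10 parameters. At 10 events per parameter (a rule of thumb), 288 events support about 28 parameters and 60 support 6.
- Bleeding ADRs: 0.004 × 3,000 = 12. Among 300 users with no drug effect: 1.2 expected, and the chance of none is 0.996^300 = 30%.

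**The case against.** The strongest reply is that this is a descriptive survey. Protocol 10.4.2 asks for incidence to be compiled; it does not promise to identify causes. Two superseded SAP versions planned Fisher and Mann-Whitney tests with 95% intervals in 2.4.8, Ver. 3.0 kept only the intervals, and the current text has neither. There is no test, no risk ratio and no rule for declaring a factor. This stands. A reader might infer that the plan will report antithrombotic use as a risk factor, or that it fails the survey's own question. The documents do not support that: no such declaration is planned, and Protocol 3.2 aims only at a limited assessment. What remains is that crude contrasts under that heading invite misreading.

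A reader might also infer that the SAP never crosses two factors. It does so once, for anticoagulant by antiplatelet use, though this does nothing about age.

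The size of the bias rests wholly on assumed inputs. That also stands, and the bias can be negligible.

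Finally, it is tempting to fit one model with every factor and base all statements on it. The documents do not guarantee the event count for that, since 9.6% comes from pre-approval studies. Moreover, antithrombotic treatment may be a consequence of cardiac or cerebrovascular disease, so mutually adjusted coefficients are not total effects. Adjustment also cannot repair timing: the SAP counts concomitant use at any time in the period, so it may begin after the ADR.

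**Conclusion.** The point holds as a modest one. The plan offers only crude ADR rates by factor, and no planned table separates antithrombotic use or organ complications from age. Under the assumed age splits (60 to 80% versus 35 to 40% aged 65 or over) and age effects (1.5 to 3 times), an antithrombotic factor with no effect would show a crude risk ratio of about 1.08 to 1.53. In the central case, 11.8% versus 9.4%, the spurious difference is of the same order as sampling error. With weaker correlation or a weaker age effect it is negligible.

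The documents do not show that the bias will occur, only that the planned tables could not reveal it. A simple stratified estimate is worth adding because it is cheap and bears on a comparison the survey says it wants to assess. Its absence does not invalidate the survey.

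**What to change.** 1. Keep the crude rates in SAP 2.4.8 and label them unadjusted.
2. Add, for patients with any ADR, a Mantel-Haenszel risk ratio with 95% CI, stratified by the SAP's three age groups and sex. Do this for antithrombotic use (Yes/No) and for liver, kidney, cardiac and cerebrovascular complications, and label it exploratory. It remains usable if ADRs are much rarer than 9.6%, with wide intervals.
3. Treat a multivariable model as optional, to be fitted only if the observed number of patients with an ADR supports it. State in the SAP that its coefficients are not to be read as the total effect of each factor.
4. For bleeding ADRs, fit no model. Beside 2.4.21, show antithrombotic Yes/No counts within under 65 and 65 or over, as description only; some cells will be nearly empty.

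The cost is a little programming on data already held and slightly wider intervals than the crude contrast would have. Confounding by underlying disease, and the timing of concomitant use, remain and should be stated as limitations.

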10.5 Efficacy Items

Compile the following regarding the efficacy-evaluable population.

10.5.1 Changes in Lipid Parameters: TG, TC, LDL-C, HDL-C, Non-HDL-C, etc.

Tabulate observed values and changes (observed value at each observational timepoint after baseline minus observed value at baseline) at each observational timepoint for TG, TC, LDL-C (by converted value calculated by direct measurement, Friedewald formula*), HDL-C, Non-HDL-C (converted value**), VLDL cholesterol, Apo-AI, Apo-B, Apo-CIII, lipoprotein (a), and RLP-C.

*: $LDL-C = TC - HDL-C - TG / 5$

**: $Non-HDL-C = TC - HDL-C$

Note that LDL-C, Non-HDL-C, TC/LDL-C ratio, LDL-C/HDL-C ratio, and LDL-C/Apo-B ratio should be calculated from test results.

10.5.2 Factors Likely to Affect Efficacy

Compile TG values by stratification variables: patient baseline characteristics (sex and age) and treatment regimen (administration of the Drug, administration of concomitant medications, etc.).

[figure not shown]

13.0 Other Necessary Items

13.1 Protocol Revision

During the surveillance period, keep track of, e.g., the progress of the Study, the onset of unexpected ADRs or serious ADRs based on the precautions, presence or absence of increased incidence of specified ADRs, the appropriateness of survey items. If needed, review and revise this protocol. If partial change approval is obtained for dosage and administration or indications during the surveillance period, examine whether to revise this protocol if necessary and revise it if necessary.

13.2 Action Taken in Case of Problem or Question

If any problem is found in the safety or efficacy of the Drug, carefully review the data and examine what needs to be done.

Appendix Study Schedule

Survey Item		Survey and Data Entry Timing		Observation Period				
		Patient enrollment	Baseline	Month 3	Month 6	Month 9	Month 12	Discontinuation
Patient Enrollment	Prescription date of the Drug	○						
Patient Enrollment	Patient ID number	○						
Patient Enrollment	Patient initials	○						
Patient Enrollment	Sex	○						
Patient Enrollment	Birth date	○						
Patient Enrollment	Inclusion criteria/exclusion criteria	○						
Patient Demographics	Height, Weight		○					
Patient Demographics	Time of hyperlipidemia diagnosis		○					
Patient Demographics	Treatment category		○					
Patient Demographics	Menopausal status (only for female)		○					
Patient Demographics	Complications		○					
Patient Demographics	Medical history		○					
Patient Demographics	Hypersensitivity disposition		○					
Patient Demographics	Drinking history, smoking history		○					
Patient Demographics	Presence or absence of surgery before baseline		○					
Patient Demographics	Presence or absence of healthier lifestyle education (diet and exercise therapies)		○					
Treatment Information	Administration of the Drug			○				○
Treatment Information	Administration of other antihyperlipidemic drugs			○				○
Treatment Information	Administration of concomitant medications (other than antihyperlipidemic drug)			○				○
Testing /Observation Items	TG		○	○	○	○	○	○
Testing /Observation Items	TC		○	○	○	○	○	○
Testing /Observation Items	LDL-C (direct measurement)		○	○	○	○	○	○
Testing /Observation Items	HDL-C		○	○	○	○	○	○
Testing /Observation Items	VLDL-C		○	○	○	○	○	○
Testing /Observation Items	Apo-AI		○	○	○	○	○	○
Testing /Observation Items	Apo-B		○	○	○	○	○	○
Testing /Observation Items	Apo-CIII		○	○	○	○	○	○
Testing /Observation Items	Lipoprotein (a)		○	○	○	○	○	○
Testing /Observation Items	RLP-C		○	○	○	○	○	○
Testing /Observation Items	FBG		○	○	○	○	○	○
Testing /Observation Items	HbA1c		○	○	○	○	○	○
Testing /Observation Items	Pregnancy status (only for female)			○				○
Testing /Observation Items	AE			○				○

○: Surveyed, tested, or observed ← ○: → Surveyed, tested, or observed throughout the period

Special Drug Use Surveillance Protocol
Lotriga Granular Capsules Special Drug Use
Surveillance
[Long-term use survey]

Version No. **6th Version**
Date Prepared **June 2, 2017**
Study Sponsor **Takeda Pharmaceutical Company Limited**

Table of Contents

1.0	Background	1
2.0	Objective	1
3.0	Target Sample Size and Rationale for Sample Size Setting	1
3.1	Target Sample Size	1

1.0 Background

Lotriga Granular Capsules (the “Drug”) is an oral capsule formulation containing the active ingredient omega-3 fatty acid ethyl esters (principally EPA-E and DHA-E). The Drug differs from general marine oil products, such as supplements, in containing a high concentration of omega-3 fatty acid ethyl esters. Since first approved in Norway in September 1994, the Drug has been in extensive use overseas, sold in more than 60 countries. In the clinical study of the Drug conducted in Japan in patients with hypertriglyceridemia, adverse drug reactions (ADRs) including ‘laboratory test abnormal’ were observed in 91 (9.6%) of the 948 patients administered at 2 g or 4 g of omega-3 fatty acid ethyl esters, and the major ADR was Diarrhea (2.5%).

Despite the proven track record of extensive use overseas and the fact that the safety of long-term use was already evaluated during the clinical study, it is important to evaluate the safety of long-term use of the Drug in the general patient population in Japan.

Special drug use surveillance (hereinafter the "Study") has been therefore designed to evaluate the safety and efficacy of long-term use of the Drug in patients with hyperlipidemia in a routine clinical setting.

